4.2 Exclusion Criteria

Patients who meet any of the following criteria will be excluded from the study.

- 1. Histologic variants other than adenocarcinoma in the primary tumor
- 2. Abnormal liver functions consisting of any of the following:
 - a) Serum bilirubin $\ge 1.5 \text{ x ULN}$

b) AST and ALT $> 2.5 \times ULN$

- 3. Therapy with other hormonal therapy, including any dose of Ketoconazole, finasteride (Proscar), dutasteride (Avodart) any herbal product known to decrease PSA levels (eg, Saw Palmetto and PC-SPES) within 4 weeks of study drug.
- 4. Requirement for corticosteroids greater than the equivalent of 7.5 mg of prednisone daily.
- 5. Therapy with samarium or strontium within 8 weeks prior to first dose of study drug.
- 6. Active infection or concomitant illness that is not controlled with medical management.
- 7. Prior radiation therapy completed < 4 weeks or single fraction of palliative radiotherapy within 14 days prior to first dose of study drug.
- 8. Any "currently active" second malignancy, other than non-melanoma skin cancer. Patients are not considered to have a "currently active" malignancy, if they have completed therapy and are considered by their physician to be at least less than 30% risk of relapse over next 3 months.
- 9. Active psychiatric illnesses/social situations that would limit compliance with protocol requirements.
- 10. Active or uncontrolled autoimmune disease that may require corticosteroid therapy during study
- 11. Severely compromised immunological state, including being positive for the human immunodeficiency virus (HIV)
- 12. Acute or chronic hepatitis B or C
- 13. Chemotherapy and other investigational therapies (targeted or immunotherapy) will require a 4-week washout period before treatment initiation
- 14. Initiation of bisphosphonate therapy within 4 weeks prior to first dose of study drug. Patients on stable doses of bisphosphonates that show subsequent tumor progression may continue on this medication; however, patients are not allowed to initiate bisphosphonate therapy during the study.
- 15. Impaired cardiac function or clinically significant cardiac diseases, including any of the following:
 - a. History or presence of serious uncontrolled ventricular arrhythmias or presence of atrial fibrillation
 - b. Clinically significant resting bradycardia (< 50 beats per minute)
 - c. LVEF assessed by 2-D echocardiogram (ECHO) < 50% or lower limit of normal (whichever is higher) or multiple gated acquisition scan (MUGA) < 45% or lower limit of normal (whichever is higher)

- d. Any of the following within 6 months prior to study entry: myocardial infartction (MI), severe/unstable angina, Coronary Artery Bypass Graft (CABG), Congestive Heart Failure (CHF), Cerebrovascular Accident (CVA), Transient Ischemic Attack (TIA), Pulmonary Embolism (PE).
- e. Uncontrolled hypertension defined by an SBP>150 and/or a DBP>100 mm Hg with or without anti-hypertensive medication.
- f. Previous pericarditis; clinically significant pleural effusion in the previous 12 months or current ascites requiring 2 or more interventions per month.
- 16. History of pituitary or adrenal dysfunction
- 17. History of gastrointestinal disorders (medical disorders or extensive surgery) which may interfere with the absorption of the study drug.
- 18. Prior therapy with TKI258
- 19. Any acute toxicities due to prior chemotherapy and/or radiotherapy that have not resolved to a NCI CTCAE (version 3.0) grade of \leq 1. Chemotherapy induced alopecia and grade 2 neuropathy is allowed.
- 20. Condition or situation which, in the investigator's opinion, may put the patient at significant risk, may confound the study results, or may interfere significantly with the patient's participation in the study.
- 21. Men whose partner is a woman of child-bearing potential, (i.e. biologically able to conceive), and who is not employing two forms of highly effective contraception. Highly effective contraception (e.g. male condom with spermicide, diaphragm with spermicide, intra-uterine device) must be used by both sexes during the study and must be continued for 8 weeks after the end of study treatment. Oral, implantable, or injectable contraceptives may be affected by cytochrome P450 interactions, and are therefore not considered effective for this study. Women of child-bearing potential is defined as sexually mature women who have not undergone a hysterectomy or who have not been naturally postmenopausal for at least 12 consecutive months (e.g., who has had menses any time in the preceding 12 consecutive months).

5.0 STUDY TREATMENT(S)

5.1 TKI258 dose and schedule

Patients will receive a single daily oral dose of of TKI258 for 5 consecutive days, followed by a 2-days rest period. Following an initial 4-week cycle at a starting dose of 400 mg 5 days- on and 2 days off, TKI258 may be escalated to 500 mg/day 5 days-on/2 days off if no significant Grade3/4 AEs or laboratory abnormalities are observed. The dose of TKI258 is NOT individually adjusted by weight or body surface area. TKI258 should be ingested with sufficient amount of water at least 1 hour prior to a meal (breakfast) or at least 2 hours following a meal (breakfast). Alternatively, TKI258 may be taken with a. low-fat meal of \leq 500 calories with \leq 20 grams fat.

Treatment cycle

A cycle is arbitrary defined as 28 days (4 weeks) for the purposes of scheduling procedures and evaluations.

A complete treatment cycle is defined as 28 days or 4 weeks.

- TKI258 if given on days 1-5, 8-12, 15-19, 22-26 (5 days on/2 days off) of each cycle.
- The first administration of TKI258 defines Day 1 of the cycle. The last day of a complete cycle is Day 28.

5.2 Permitted study drug adjustments

5.2.1. Dosing schedule.

The decision whether to continue with study drug should be based on individual circumstances and the physician's judgment that continuation is in the patient's best interest. If the study treatment is interrupted, because of its toxicity or a lack a compliance to the treatment schedule by the patient, the following guidelines should apply.

- If TKI258 is taken on a "rest days", then the patient will resume the original 5 days on/2 days off schedule starting with the next day of dosing as follows: if the patient takes an additional dose on Day 6, then the patient will rest on Day 7 and start the 5 days on/2 days off dosing on Day 1; if patient takes a dose on Day 7, then the patient will skip Day 1 of the 5 days on/2 days off and start dosing the following day (Day 2). If patient takes a dose on Day 6 and 7, then the patient will skip Day 1 and 2 of the 5 days on/2 days off and start dosing the following day (Day 3).
- If the patient missed TKI258 dose on Day 1, 2, 3 or 4, he should restart TKI258 the next dosing day and rest on Days 6 and 7
- If the patient missed TKI258 dose on Day 5, 6, 7, he should rest on Days 6 and 7 and restart TKI258 on Day 1 of the next week.

Regardless of the reason for the delay in study treatment, patient must discontinue study treatment when the interval between 2 administrations of treatment exceeds 21 days.

These changes must be recorded on the Dosage Administration Record of the electronic Case Report Form (eCRF).

5.2.2 Dosing modifications.

For patients who are unable to tolerate the protocol-specified dosing schedule of TKI258, dose reduction is permitted to a minimum of 300 mg Table 5-1:

Table 5-1Dose reduction steps for TKI258

Dose reduction*					
	Dose level - 0	Dose level - 1	Dose level - 2		
TKI258	500 mg	400 mg	300 mg**		
*Dose reduction should be based on the worst toxicity demonstrated at the last dose.					
**Dose reduction below 300 mg is	not allowed.				

Grade 3 (> 3.0 - 10.0 x ULN) Grade 4 (> 10.0 x ULN)	Discontinue study treatment Note: If Grade 3 or Grade 4 hyperbilirubinemia is due to the indirect component only, and hemolysis as the etiology has been ruled out as per institutional guidelines (e.g. review of peripheral blood smear and haptoglobin determination), then \downarrow 1 dose level and continue treatment at the discretion of the investigator. Discontinuation of study treatment is required if concurrent elevations of total bilirubin > 2.0 X upper limit of normal (ULN) and ALT or AST > 3.0 X ULN are observed. In order to characterize hepatic toxicity more precisely, fractionation of bilirubin and alkaline phosphatases will be required for elevated values > 2.0 X ULN and \geq CTCAE grade 2, respectively.
AST or ALT	
Grade 1 (> ULN - 2.5 x ULN) Grade 2 (> 2.5 - 5.0 x ULN)	Maintain dose level
Grade 3 (> 5.0 - 20.0 x ULN)	Delay study treatment until resolved to \leq grade 1 (or \leq grade 2 if liver infiltration with tumor present), then If resolved by \leq 7 days after suspending TKI258, maintain dose level If resolved by > 7 days after suspending TKI258, \downarrow 1 dose level Discontinuation of study treatment is required if concurrent elevations of total bilirubin > 2.0 X upper limit of normal (ULN) and ALT or AST > 3.0 X ULN are observed. In order to characterize hepatic toxicity more precisely, fractionation of bilirubin and alkaline phosphatases will be required for elevated values > 2.0 X ULN and \geq CTCAE grade 2, respectively.
Grade 4 (> 20.0 x ULN)	Delay study treatment until resolved to \leq grade 1, then \downarrow 1 dose level

Cardiac	
Hypertension	Treatment-emergent hypertension should be treated as per standard cardiology practice. Recommended agents for the management of blood pressure elevations on TKI258 include angiotensin-converting enzyme inhibitors and calcium channel blockers.
Grade 1	Maintain dose level
Grade 2 / 3	 Delay the study treatment and initiate/intensify antihypertensive therapy. TKI258 may be restarted in conjunction with standard anti-hypertensive medication if BP is controlled (i.e BP ≤ 150/100 mmHg).
	If BP is controlled \leq 7 days after suspending TKI258, maintain dose level
	If BP is controlled > 7 days after suspending TKI258, $\downarrow 1$ dose level
Grade 4	Delay the study treatment and initiate/intensify antihypertensive therapy. \downarrow 1 dose level TKI258 may be restarted in conjunction with anti- hypertensive medication if BP is controlled (i.e BP \leq 150/100 mmHg).
Cardiac – Other	
Grade 1 or 2	Maintain dose level
Grade 3	Delay study treatment until resolved to \leq grade 1, then \downarrow 1 dose level
Grade 4	Discontinue study treatment
Gastrointestinal	
Diarrhea	At the first sign of abdominal cramping, loose stools, or onset of diarrhea, it is recommended that the patient be treated according to institutional standard of care
Grade 1 (despite maximal anti- diarrheal medication)	Maintain dose level
Grade 2 (despite maximal anti- diarrheal medication)	Delay study treatment, until resolved to \leq grade 1, then restart at the current dose level. If diarrhea returns as \geq grade 2, then suspend dose until resolved to \leq grade 1, then \downarrow 1 dose level
Grade 3/4 (despite maximal anti-diarrheal medication)	Delay study treatment until resolved to \leq grade 1, then \downarrow 1 dose level
ineurotoxicity	

\geq 1 CTCAE grade level	Grade $0 \rightarrow$ Grade 1: maintain dose level		
increase	Grade 0 or $1 \rightarrow$ Grade 2 : delay study treatment until		
	resolved to \leq grade 1, then \downarrow 1 dose level		
\geq CTCAE grade 3	Discontinue study treatment		
Hypertriglyceridemia and/or hype	ercholesterolemia		
Grades 1, 2 or asymptomatic grade 3	Maintain dose level. Initiation or adjustment of an existing triglyceride-and/or cholesterol-lowering agent will be at the discretion of the investigator.		
Grade 3 with symptoms or grade 4	Delay study treatment and initiate/ optimize triglyceride- and/or cholesterol-lowering therapy.		
	If the toxicity returns to \leq grade 3 without symptoms by \leq 14 days, treatment with TKI258 may resume at the same dose level.		
	At the re-occurrence of grade 3 with symptoms or grade 4 toxicity. If within 14 days the patient returns to \leq grade 3 without symptoms, dosing with TKI258 may resume at the next lower dose level		
	If toxicity does not returns to \leq grade 3 without symptoms within 14 days, discontinue study treatment.		
Amylase and/or lipase elevations			
Grade 1 or 2	Maintain dose level		
Asymptomatic grade 3 or 4	Delay TKI258 and evaluate at least twice weekly until \leq grade 2 then restart at current dose level. If levels have not returned to \leq grade 2 within 3 weeks then no further TKI258 may be given and the patient should discontinue permanently from the study. A CT scan or other imaging study to assess the pancreas, liver and gallbladder must be performed within 1 week of the first occurrence of any grade 3 elevation of amylase and/or lipase.		
Symptomatic grade 3 or 4	TKI258 must be stopped immediately and proper medical intervention taken. Evaluate at least twice weekly until resolution to \leq grade 1. Clinical manifestations should be monitored as needed until resolution or stabilization of the disease condition. No further TKI258 may be administered.		
Pancreatitis			
Grade 1	Maintain dose level		
Grade 2, 3 or 4	Discontinue study treatment.		
Other adverse events			
Grade 1 or 2	Maintain dose level		
Grade 3	Delay dose until resolved to \leq grade 1, then \downarrow 1 dose level		

Grade 4	Discontinue TKI258
	Suspend dose for \geq CTCAE grade 3 vomiting or nausea only if it could not be controlled despite the use of standard anti-emetics.

All dose modifications should be based on the worst preceding toxicity.

Isolated values of \geq grade 3 alkaline phosphatase values will NOT require dose interruption.

 \geq Grade 3 anemia judged to be a hemolytic process secondary to study drug will require discontinuation of study treatment.

 \geq Grade 3 lymphopenia considered clinically significant will require dose interruption until resolved to \leq grade 1, then \downarrow dose level.

Patients are allowed two dose reductions. If a patient requires a dose interruption of > 21 days, then the patient must be discontinued from the study. Patients who discontinue the study for a study related adverse event or abnormal laboratory value must be followed at least once a week for 28 days and subsequently at 28 day intervals until resolution or stabilization of the event, whichever comes first.

^{a.} Common Terminology Criteria for Adverse Events (CTCAE Version 3.0) otherwise specified values.

5.3 Restrictions

5.3.1 Patients must be instructed not to take additional medications including overthe-counter products and herbal/alternative medications during the study without prior consultation with the investigator. It is important to avoid concomitant medications that are known to cause hepatotoxicity.

Oral contraceptives are generally metabolized by CYP3A4/2C9, and act also as a moderate inhibitor of CYP1A2, therefore should not be used. Thus, patients who are sexually active and are using oral contraceptives as a method of contraception, should change to two highly effective contraceptive methods during the study participation.

Permitted treatments during the study include, but are not limited to the following:

- Pain medication to allow the patient to be as comfortable as possible
- Localized radiotherapy and treatment with bisphosphonates for pre-existing, painful bone metastases is permitted only if evidence of radiological progression is not present. Treatment with bisphosphonates must begin before the study treatment is initiated.
- Nutritional support or appetite stimulants (e.g. megestrol)
- Oxygen therapy and blood products or transfusions
- Prophylactic anti-emetics are allowed for patients who, at the discretion of the investigator, have experienced ≥ grade 1 nausea or vomiting.
- Hematopoietic growth factors should be used according to the guidelines established by the American Society of Clinical Oncology (ASCO) or as dictated

by local practice. The ASCO guidelines are available [http://jco.ascopubs.org/cgi/content/full/24/19/3187]

The administration of anticoagulation and antiaggregation agents (e.g. eptifibatide, epoprosterol, prasugrel, dipyridamole, fondaparinix) should be allowed except prasugrel, due to its potential drug-drug interaction with either sorafenib or TKI258. Prasugrel is primarily metabolized by the CYP3A4 and CYP2B6 and to a lesser extent by the CYP2C9 and CYP2C19. Co-administration of prasugrel with sorafenib could increase the systemic exposure of parsugrel, since sorafenib could inhibit CYP2B6. In addition, in vitro study demonstrated that TKI258 is an inducer of CYP2C9 and CYP2C19, co-administration of TKI258 with parsugrel is likely to reduce the exposure of parsugrel. For oral anticoagulants, the upper limit of INR is < 1.5.

The following concomitant treatments are not allowed during the study:

- Concurrent use of isoniazid, labetolol, trovafloxacin, tolcapone, and felbamate are not permitted, since alternative less hepatotoxic drugs are available to use.
- Concurrent use of other investigational drugs is not permitted.
- The administration of other antineoplastic therapy (e.g. chemotherapy, hormone therapy, immunotherapy, targeted therapy, monoclonal antibodies and radiation therapy) is not permitted. Patients requiring radiation therapy after the start of the study are considered as having progression of disease and must discontinue study treatment.

5.3.2 Concomitant therapy with the following is **prohibited**:

- Chemotherapy
- Multifraction radiation therapy
- Immunotherapy
- Radiopharmaceuticals such as strontium (⁸⁹Sr) or samarium (¹⁵³Sm)

Patients who require the use of any of these therapies will be discontinued from study-treatment, entered into long-term follow-up for overall survival assessments. Patients who discontinue from the study will be followed for safety outcomes for **30 days** following the patient's last dose or until the patient receives another anticancer therapy, whichever occurs first.

5.3.3 Concomitant therapy with the following is **restricted**:

- 5 α -reductase inhibitor
- Ketoconazole, diethylstilbestrol, PC-SPES, and other preparations such as saw palmetto thought to have endocrine effects on prostate cancer
- Potent inhibitors/inducers of the following CYP450 enzymes including quinidine (a CYP2D6 inhibitor), fluvoxamine (CYP1A inhibitor), omeprazole (a CYP1A inducer), ketoconazole, itraconazole, erythromycin and glibenclamide (CYP3A4 inhibitors), as well as phenobarbital, phenytoin, carbamazepine and rifampicin (all CYP3A4 inducers), should be

used with caution. A comprehensive list of medications that inhibit, induce, and/or are metabolized by the various CYP 450 enzyme isoforms can be found at http://medicine.iupui.edu/flockhart. See also, Appendix H.

The decision to administer a restricted therapy should be made based on the consideration of the safety of study participant. Such therapies will be used with careful monitoring.

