6.9 Removal of Patients from the Study or Study Drug

6.9.1 The investigator must withdraw a patient from study treatment or the study for any of the following reasons:

- Progressive disease. As clinical benefit may be independent of PSAmodulation, progressive disease will not be defined by PSA criteria alone. Rather progressive disease will be defined as any skeletal related event (6.9.2) or tumor progression as defined by RECIST criteria (Appendix I) accompanied by PSA progression or investigator defined clinical progression:
- A serious or intolerable AE occurs as described in 6.7.
- The sponsor or investigator terminates the study.
- The patient requests to be discontinued from the study.

6.9.2 Definition of skeletal-related events (SREs) consisting of the following discrete clinical events or unequivocal radiological changes related to underlying disease progression:

- Progression by radionuclide bone scan with 2 or more new lesions. If progression is noted at the first assessment (ie, Week 12), then a confirmation by a second scan is required 6 or more weeks later that shows a minimum of 2 or more additional new lesions.
- Pathologic bone fracture in the region of cancer involvement that occur spontaneously or as the result of trivial trauma. Each pathologic fracture (vertebral and non-vertebral is to be documented by appropriate diagnostic imaging.
- Radiation therapy to bone radiation administered to bone to palliate painful lesions or prevent or treat pathologic fractures or spinal cord compression.
- Administration of a radioisotope, such as strontium 89, will be included as radiation to bone.
- Cancer-related surgery to bone procedures that are performed to set or stabilize pathologic fractures or areas of spinal cord compression, and surgical procedures that are performed to prevent a pathologic fracture or spinal cord compression.
- Spinal cord or nerve root compression these will be confirmed by MRI. If spinal cord compression occurs in conjunction with vertebral compression, each will be counted seapartely.

6.9.3. Tumor progression as defined by RECIST criteria (see Appendix I).

Bone lesions will not be considered measurable for purposes of RECIST evaluation of disease.

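### Section 5.3.1 both permits localized radiotherapy to pre-existing painful bone metastases during the study and requires any patient needing radiotherapy after study start to stop treatment as a progressor

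*Combined protocol and SAP*

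**What the plan says.** Radiotherapy during the study is addressed in four places.

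- **Section 5.3.1, permitted list.** The list is introduced by "Permitted treatments during the study include, but are not limited to the following". One bullet reads "Localized radiotherapy and treatment with bisphosphonates for pre-existing, painful bone metastases is permitted only if evidence of radiological progression is not present". The next sentence in that bullet sets a timing limit: "Treatment with bisphosphonates must begin before the study treatment is initiated".
- **Section 5.3.1, not-allowed list.** The bullet on other antineoplastic treatment names radiation therapy among the barred modalities and ends: "Patients requiring radiation therapy after the start of the study are considered as having progression of disease and must discontinue study treatment".
- **Section 5.3.2, prohibited list.** One entry is "Multifraction radiation therapy". Therapeutic radioisotopes are listed too. Patients who need anything on this list come off study treatment and enter long-term survival follow-up. Single-fraction radiotherapy is not mentioned.
- **Sections 6.9.1 and 6.9.2.** Progressive disease is a ground for compulsory withdrawal, and its definition includes skeletal-related events. One such event is "radiation administered to bone to palliate painful lesions or prevent or treat pathologic fractures or spinal cord compression". The opening sentence of 6.9.2 limits these events to those tied to progression of the underlying disease.

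**The concern.** The two lists in 5.3.1 follow one another in the same subsection. One lets a patient have localized radiotherapy during the study; the other declares a patient who needs radiotherapy to have progressed and takes him off the drug. The second sentence has no carve-out for the first, and neither list refers to the other.

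Skeletal metastasis is an inclusion criterion (Section 4.1), so palliative radiotherapy to bone is foreseeable in any enrolled patient. Treatment runs until progression (Synopsis and Section 3.2), so the rule applied sets the length of exposure. Stopping early can also take a patient out of the four-weekly PSA tests (7.4.1), the urine N-telopeptide and bone alkaline phosphatase schedule (7.4.3) and the marrow sampling at 7 to 10 weeks (7.4.5). PSA response is a primary outcome, and the marker and marrow results supply covariates for the models in Section 10.0.

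**Working it through.** The plan states no figure on this point and no formula applies. The check follows one patient through each rule.

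**Test case.** A patient on TKI258 has a painful bone metastasis that was present at entry. Imaging shows no progression. He needs localized radiotherapy to that lesion.

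1. *5.3.1, permitted list.* All its conditions are met. The radiotherapy is allowed and gives no reason to stop the drug.
2. *5.3.1, not-allowed list.* He needs radiation after study start. He counts as a progressor and must stop.
3. *5.3.2.* If the course is multifraction, he must stop. If it is a single fraction, the section is silent.
4. *6.9.1/6.9.2.* Radiation to palliate a painful bone lesion is a listed skeletal-related event. Whether it counts here depends on whether it is judged to relate to disease progression. If it counts, 6.9.1 points to progression and withdrawal. However, the wording of 6.9.1 leaves open whether accompanying PSA or clinical progression is required for skeletal-related events or only for RECIST progression.

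Steps 1 and 2 give opposite outcomes for the same patient. Steps 3 and 4 do not decide between them.

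**Readings that might remove the conflict.**

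- *The permission covers only radiotherapy begun before the study.* The list concerns treatment during the study, and the start-before condition names bisphosphonates alone.
- *The bar covers only radiotherapy given with antineoplastic intent.* The first sentence of that bullet could be read so. The sentence on progression and discontinuation has no such limit.
- *The number of fractions separates the rules.* Exclusion criterion 7 in Section 4.2 does single out single-fraction palliative treatment, but neither 5.3.1 list nor 6.9.2 uses the distinction.

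**Scale.** The documents give no rate of palliative bone radiotherapy and no share of patients who would meet the permitted list's conditions. The only arithmetic available is the weight of one patient: 1/40 = 2.5% of planned enrolment. Section 10.0 expects about 60% positive biopsies, so 0.60 × 40 = 24 patients. One of those is 1/24, or about 4.2%, if marrow analyses depend on a positive biopsy (an assumption).

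**The case against.** The strongest defence is that the permission is a specific exception and the bar a general rule. The barring bullet is about other anticancer treatment, the permitted bullet is about symptom relief in known lesions, and a specific provision ordinarily governs a general one. On this view only a cross-reference is missing. That is a plausible account of what was intended, but the text does not say it, and the discontinuation sentence is worded as an absolute requirement. Investigators could reasonably act either way.

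Four further points on the other side stand and limit the finding.

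- A reader might infer that four places give several mutually contradictory rules. The documents do not support that. Section 5.3.2 does not say that multifraction treatment is the only radiotherapy prohibited, and its silence on a single fraction is not permission. Section 6.9.2 can be read consistently with the permitted list, because its opening sentence ties events to underlying progression. The clear clash is between the two 5.3.1 lists; the other sections add ambiguity.
- A reader might infer that all localized radiotherapy is affected. The permission is conditional. For a new lesion, or with radiological progression, it does not apply and the two lists do not conflict.
- A reader might infer that the survival outcome is compromised. Sections 5.3.2, 7.6 and 8.0 keep patients in survival follow-up after treatment stops, so deaths are still captured. An effect through later therapy is conjecture.
- A reader might infer bias in a progression-based analysis. Sections 2.0 and 10.0 plan no progression-free survival or time-to-progression analysis. The PSA-only progression timing in Section 10.0 does not involve radiotherapy.

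The final visit in 7.5, within four weeks of stopping the drug, includes PSA, urine N-telopeptides and marrow, which offsets part of any loss. It is not a full substitute for samples taken on treatment.

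**Conclusion.** The contradiction within Section 5.3.1 is real. It is confined to patients who need localized radiotherapy for a pre-existing painful bone metastasis without radiological progression. For them the plan both allows treatment to continue and requires it to stop, and nothing elsewhere in the document resolves this.

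The direct consequences are inconsistent time on drug and inconsistent progression status. A possible further consequence is loss of on-treatment PSA and bone-marker data, and of the week 7 to 10 marrow sample if the radiotherapy comes before it. The number of patients cannot be estimated from the documents. The sample size of 40, the Bayesian survival criterion and the toxicity stopping rule do not depend on the point.

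The conclusion rests on reading the discontinuation sentence as written, without an implied exception. It does not depend on Section 6.9. It should be corrected as an internal inconsistency in the treatment rules; it is not a flaw in the primary survival analysis.

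**What to change.** The sponsor should reconcile the permitted and not-allowed lists in 5.3.1, the prohibited list in 5.3.2, and 6.9.1/6.9.2 into one rule. It should state which radiotherapy is compatible with continued study treatment and which counts as progression requiring discontinuation. Each section should then repeat or cross-refer to that rule, and any intended exception should be written out.

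In 6.9.1 the text should make clear whether accompanying PSA or clinical progression is required for skeletal-related events as well as for RECIST progression. The rule should be applied uniformly to discontinuation and to recorded progression status. This review takes no view on which rule is clinically right.

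The cost is a wording amendment. No new data, visits or patients are needed.
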